#### 3.4 Analysis Populations

All Screened: All subjects who were consented and screened for the study.

All Enrolled: All Screened subjects except for screen failures (who haven't met study eligibility criteria).

Treated with Caya: All Enrolled subjects who have used the Caya® in the study.

Treated with Ovaprene: All Enrolled subjects who have used the Ovaprene® in the study.

Treated with Ovaprene with at Least One PCT Cycle: All Enrolled subjects who have used the Ovaprene® and completed one or two PCT cycles in the study.

"Treated with Ovaprene" is a sub-set of "Treated with Caya", whereas all used Ovaprene® device subjects also used Caya® device, but not vice versa. Since Ovaprene® is the target study device, most analyses will be using "Treated with Ovaprene" and "Ovaprene with at Least One PCT Cycle" populations. In the summary tables, "Treated with Caya" and "Treated with Ovaprene" analysis populations will be simply labeled as "Caya Population" and "Ovaprene Population", respectively.

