#### 3.6 Efficacy Analysis

All efficacy analyses will be done for the Ovaprene with at Least One PCT Cycle population, and may be repeated for Treated with Caya population when necessary. The primary efficacy analysis will be the changes in PCT results due to Ovaprene® device use, and consists of the following 6 endpoints:

a) The proportion (and 95% exact binomial confidence interval ) of subjects with an average of fewer than 5 progressively motile sperm per HPF in cervical mucus, after sex at ovulation in the absence of the device. This needs to use the "Average number of progressively motile sperm" (SAS variable name MUAVPMS) in Cervical Mucus CRF, and count the number of subjects with MUAVPMS < 5.0 at the Visit 3 (BP2); then divided by the total number of subjects with PMS measurements at this visit, and finally converted to a percentage (multiplied by 100). In the data listing of PMS data, the data that occur in a cycle after a dislodgement in the e-diary, and clinician noted dislodgement, will be flagged.

This primary efficacy analysis will be repeated by subgroups for:

- (1) Had vaginal ring use before enrolling in the study vs. Never had
- (2) Had vaginal delivery vs. caesarean birth
- (3) BMI ≥30 (Obese) vs. <30 at Baseline
- (4) Study site EVMS vs. Non-EVMS study sites
- (5) Device position at the time PCT: Over cervical os, Not over cervical os on anterior vaginal wall, Not over cervical os and not on anterior vaginal wall

- (6) Dislodgments (dislodgement reported in cycle before the PCT visit vs. no dislodgements reported in cycle before PCT).
- b) The sample size, mean, median, standard deviation, and interquartile range (IQR, i.e., 25th and 75th percentiles), for the average number (across 9 HPFs) of progressively motile sperm per HPF in cervical mucus, across all treated subjects, in the absence of the device. This is to summarize the same field (MUAVPMS) in the above Bullet a) as a continuous variable at Visit BP2.
- c) The proportion of subjects (and 95% exact binomial confidence interval) with an average of fewer than 5 progressively motile sperm per HPF in cervical mucus, in the presence of the Ovaprene® device. This is similar to that in Bullet a), but will be done at Visit OP3A, and at Visit OP3B, by sub-setting the CRF data at VISIT\_ID = 14, and at VISIT\_ID = 19, respectively.

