- c) Levels of ferrous gluconate in CVF before sex that are associated with fewer than 5 progressively motile sperm per HPF in the cervical mucus after sex (i.e. success), during ovulation. Summary statistics of sample size, mean, median, standard deviation, and IQR will be presented by visit.
- d) Levels of ferrous gluconate in CVF at multiple time points in the safety cycle in the absence of coitus. This will allow the estimation of how long after insertion it takes to reach the target concentration levels associated with success and whether target levels are still present up to 29 days after insertion. Summary statistics of sample size, mean, median, standard deviation, and IQR will be presented by visit and assessment timepoint.
- e) Levels of ferrous gluconate in CVF before and at multiple time points after sex at ovulation with the device in place. This will allow determination of whether they are different from before sex and, if so, how much time is needed to return to pre-sex levels at all visits in Ovaprene® PCT cycles in both vaginal and cervical fluid. Summary statistics of sample size, mean, median, standard deviation, and IQR will be presented by visit and assessment time-point.
- f) Vaginal pH (from Vaginal Sample CRF) and cervical pH (from Cervical Mucus CRF) before and after sex in the absence and presence of the device. Six-number summary for the observed values and difference between pre-sex and after sex will be presented by visit. For the study site (EVMS only) with multiple timepoints at a visit, the summary will be done at each timepoint. The average of pH values within each visit over the multiple timepoints will be calculated for each subject, and then be summarized. The goal of these assessments during the Ovaprene® safety cycle is to look at the effect of study device in the absence of sex.
- g) Residual amount of ferrous gluconate in Ovaprene® devices that have been worn over a cycle of use. Six-number summary statistics will be presented by visit and by duration of time the device was worn (1-7 days, 8-14 days, 15-21 days, 22-28 days and >28 days).
- h) Cervical mucus score. Summary statistics mean, median, standard deviation, and IQR will be presented by visit. The number and percent of subjects with cervical mucus score ≥ 10 in each Ovaprene cycle will also be presented. For the summary of cervical mucus score ≥ 10, cervical mucus data will only be used from the cycle that occurs after the highest OPK result for that cycle.

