| 14.2.1.1-Dis    | Number and Percent of Subjects with an Average of Fewer Than 5 Progressively Motile Sperm per HPF in Cervical Mucus by Subjects Had Ring Dislodgement or Not            | Ovaprene with at Least One PCT Cycle |
| 14.2.1.2        | Average Number (across 9 HPFs) of Progressively Motile Sperm per HPF in Cervical Mucus and Change from Baseline Cycle to Ovaprene PCT Cycles                            | Ovaprene with at Least One PCT Cycle |
| 14.2.1.3        | Number and Percent of Ovaprene Cycles with Fewer Than 5 PMS per HPF in Cervical Mucus   | Ovaprene with at Least One PCT Cycle |
| 14.2.1.4        | Number and Percent of Subjects with Fewer Than 5 PMS per HPF in Cervical Mucus  | Ovaprene with at Least One PCT Cycle |
| 14.2.2.1-E      | Summary of the Levels of Ferrous Gluconate in CVF at Study Site EVMS  | Ovaprene with at Least One PCT Cycle |
| 14.2.2.1-E-5PMS | Summary of the Levels of Ferrous Gluconate in CVF at Study Site EVMS for Subjects with Fewer Than 5 PMS per HPF in the Cervical Mucus after Sex                         | Ovaprene with at Least One PCT Cycle |
| 14.2.2.1-NE     | Summary of the Levels of Ferrous Gluconate in CVF at Non-EVMS Sites   | Ovaprene with at Least One PCT Cycle |

| Table Number         | Table Title  | Population                    |
|----------------------|--|--------------------------------------|
| 14.2.2.1-NE-
5PMS | Summary of the Levels of Ferrous Gluconate in CVF at Non-
EVMS Sites for Subjects with Fewer Than 5 PMS per HPF in the
Cervical Mucus after Sex    | Ovaprene with at Least One PCT Cycle |
| 14.2.2.2-E           | Summary of the Levels of Ferrous Gluconate in Cervix at Study Site EVMS  | Ovaprene with at Least One PCT Cycle |
| 14.2.2.2-E-5PMS      | Summary of the Levels of Ferrous Gluconate in Cervix at Study Site EVMS for Subjects with Fewer Than 5 PMS per HPF in the Cervical Mucus after Sex       | Ovaprene with at Least One PCT Cycle |
| 14.2.2.2-NE          | Summary of the Levels of Ferrous Gluconate in Cervix at Non-EVMS Sites   | Ovaprene with at Least One PCT Cycle |
| 14.2.2.2-NE-
5PMS | Summary of the Levels of Ferrous Gluconate in Cervix at Non-
EVMS Sites for Subjects with Fewer Than 5 PMS per HPF in the
Cervical Mucus after Sex | Ovaprene with at Least One PCT Cycle |
| 14.2.2.3-E           | Summary of Cervical Mucus pH Values at Study Site EVMS   | Ovaprene with at Least One PCT Cycle |

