| 14.2.2.3-NE          | Summary of Cervical Mucus pH Values at Non-EVMS Sites  | Ovaprene with at Least One PCT Cycle |
| 14.2.2.4-E           | Summary of Vaginal Lateral Wall pH Values at Study Site EVMS   | Ovaprene with at Least One PCT Cycle |
| 14.2.2.4-NE          | Summary of Vaginal Lateral Wall pH Values at Non-EVMS Sites  | Ovaprene with at Least One PCT Cycle |
| 14.2.2.5             | Summary of Residual Amount of Ferrous Gluconate in Device  | Ovaprene with at Least One PCT Cycle |
| 14.2.2.5-Dur         | Summary of Residual Amount of Ferrous Gluconate in Device by Duration of Time the Device was Worn  | Ovaprene with at Least One PCT Cycle |
| 14.2.2.6             | Summary of Cervical Mucus Scores by Visit  | Ovaprene with at Least One PCT Cycle |
| 14.2.2.6-Ca          | Summary of Cervical Mucus Scores by Visit for Caya Population  | Caya                                 |
| 14.2.2.7             | Number and Percentage of Subjects with Cervical Mucus Score at Least 10 by Cycle   | Ovaprene with at Least One PCT Cycle |
| 14.2.2.7-Ca          | Number and Percentage of Subjects with Cervical Mucus Score at Least 10 by Cycle for Caya Population   | Caya                                 |
| 14.2.3.1             | Summary of Open-ended Acceptability Questions  | Ovaprene                             |
| 14.2.3.2             | Summary of Closed-ended Acceptability Questions  | Ovaprene                             |

| Table Number | Table Title   | Population |
|--------------|---|-------------------|
| 13.2.3.3     | Summary of Acceptability Questions by Ovaprene Device Position Based on Digital Exam  | Ovaprene          |
| 14.2.4.1A    | Shifts of Acceptability from Visit OS5 to Visit OP3A – Part A   | Ovaprene          |
| 14.2.4.1B    | Shifts of Acceptability from Visit OS5 to Visit OP3A – Part B   | Ovaprene          |
| 14.2.4.1C    | Shifts of Acceptability from Visit OS5 to Visit OP3A – Part C   | Ovaprene          |
| 14.2.4.1D    | Shifts of Acceptability from Visit OS5 to Visit OP3A – Part D   | Ovaprene          |
| 14.2.4.1E    | Shifts of Acceptability from Visit OS5 to Visit OP3A – Part E   | Ovaprene          |
| 14.2.4.2A    | Shifts of Acceptability from Visit OS5 to Visit OP3B – Part A   | Ovaprene          |
| 14.2.4.2B    | Shifts of Acceptability from Visit OS5 to Visit OP3B – Part B   | Ovaprene          |
| 14.2.4.2C    | Shifts of Acceptability from Visit OS5 to Visit OP3B – Part C   | Ovaprene          |

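### Ferrous gluconate, pH and residual-device tables cover only women who completed an Ovaprene PCT cycle, so safety-cycle values from women who stop earlier are left out of the summaries

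*SAP*

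**What the plan says.** SAP 3.4 defines two nested populations of device users. The wider, Treated with Ovaprene, is "All Enrolled subjects who have used the Ovaprene® in the study". The narrower, Ovaprene with at Least One PCT Cycle, is "All Enrolled subjects who have used the Ovaprene® and completed one or two PCT cycles in the study". What counts as completing a cycle is not defined.

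SAP 3.6 states: "All efficacy analyses will be done for the Ovaprene with at Least One PCT Cycle population". That section includes the secondary analyses of ferrous gluconate (FG) release, vaginal and cervical pH, and FG left in worn devices. One of them is "Levels of ferrous gluconate in CVF at multiple time points in the safety cycle in the absence of coitus". The only repeat it allows for is in the Caya population.

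The population column in SAP 4.2.1 follows the rule. The narrower population is given for the FG tables (14.2.2.1, beginning with "Summary of the Levels of Ferrous Gluconate in CVF at Study Site EVMS", and 14.2.2.2), the pH tables (14.2.2.3 and 14.2.2.4, for example "Summary of Vaginal Lateral Wall pH Values at Study Site EVMS") and the residual tables (14.2.2.5, "Summary of Residual Amount of Ferrous Gluconate in Device", and its version by wear time).

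Protocol 14.2 calls for an as-treated analysis. Protocol 14.2.3 asks for FG summaries at every collection time over all women.

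**The concern.** The safety cycle is Cycle 3, and the Ovaprene PCT cycles are Cycles 4 and 5. Safety-cycle FG, safety-cycle pH and the device removed at OS5 exist before any Ovaprene PCT takes place. Requiring a later completed PCT cycle therefore conditions these summaries on what happens afterwards.

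Two things are at stake. One is information: in a study of about 25 completers, each release profile counts. The other is selection. Protocol 7.5 lists adverse events, including symptomatic bacterial vaginosis, among reasons for discontinuation. If women who stop in or after Cycle 3 differ in release, pH or wear time from those who stay, the tables describe only those who stay.

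**Working it through.** The plan has no figure to reproduce: SAP 2.5 says the sample size was not set on statistical grounds, and these tables are descriptive. The check compares the texts and then gives an illustrative range.

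**Step 1: which cycles the population refers to.** The words "completed one or two PCT cycles in the study" fit the two Ovaprene PCT cycles. If the baseline or Caya PCT cycle counted, the restriction would be nearly empty, because SAP 3.4 says every Ovaprene user has also used Caya and enrolment follows a successful baseline PCT.

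**Step 2: what the affected summaries need.**

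| Summary | Data source | Needs an Ovaprene PCT? |
|---|---|---|
| Early release curve and check against 8.2 µg/mL (SAP 3.6, secondary a, b) | OS1 samples at 0.5 to 6 hours, EVMS only | No |
| FG over the safety cycle (secondary d) | OS1 to OS5 | No |
| Safety-cycle pH (part of secondary f) | OS1 to OS5 | No |
| Residual FG (secondary g) | Devices removed in Cycles 3, 4 and 5 | No |
| FG associated with fewer than 5 progressively motile sperm (secondary c; the four -5PMS tables) | Ovaprene PCT cycles | Yes |

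**Step 3: where the omission weighs most.**
- The early release curve comes from one site, so its denominator is already small.
- Residual FG is split by wear time: 1-7, 8-14, 15-21, 22-28 and over 28 days. Protocol 9.4.1 schedules safety-cycle removal 21-23 days after insertion, or sooner if menses is expected. The two shortest strata will therefore be filled mainly by early removals, and women who stop the study at that point are excluded.

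**Step 4: illustrative size.** Let k be the number of women who use Ovaprene but do not complete an Ovaprene PCT cycle. Assume 25 women in the PCT population. The share of exposed women missing from the tables is k / (25 + k).

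| k (assumed) | Treated with Ovaprene | Share omitted |
|---|---|---|
| 0 | 25 | 0% |
| 2 | 27 | 2/27 = 7.4% |
| 5 | 30 | 5/30 = 16.7% |
| 10 | 35 | 10/35 = 28.6% |
| 20 | 45 | 20/45 = 44.4% |

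The last row is a ceiling. It takes all of the 45 - 25 = 20 planned non-completers to have used Ovaprene and none to have completed an Ovaprene PCT cycle.

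**Step 5: entry to the PCT population.** An Ovaprene PCT cycle runs from OP1 to OP5. The sperm count is taken at OP3 (about day 15 in protocol Table 11), and OP5 falls at about day 28. SAP 3.6 primary bullet a divides by women with a sperm count at the visit, bullet c follows it, and bullet f counts all treated cycles with a value. None of these mentions OP5. If completion in 3.4 means attending OP5, the population rule and these denominators disagree for a woman who has an OP3A result and leaves before OP5A.

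**The case against.** The strongest reply has four parts.

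**Nothing is lost.** A reader might infer that the data are discarded. They are not: SAP 4.2.2 lists all collected data for all screened women, including vaginal samples, iron per ring and the iron assay. This stands. The gap is in the summary tables, which carry the endpoint estimates.

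**The restriction is partly sensible.** Safety-cycle FG is to be read against levels associated with PCT success, so using the same women for both has some logic. The -5PMS tables cannot be built without a PCT result. Protocol Section 6 assesses pH before and after sex only in the baseline and Ovaprene PCT cycles. The -5PMS argument stands in full. The others do not justify omitting safety-cycle values: the protocol asks for all women at each FG time point, and SAP 3.6 gives safety-cycle pH its own purpose, the effect of the device without sex.

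**The size is assumed.** This stands. Twenty-five is the number expected to complete all five cycles. The PCT population also admits women with one Ovaprene PCT cycle, so at planned completion 25 is a minimum. With 35 exposed and 28 in the PCT population, for example, the omission is 7/35 = 20.0% rather than 28.6%. Enrolment precedes the Caya cycle, so some non-completers may never use Ovaprene.

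**The primary analysis is not shown to be affected.** A reader might infer that the wording removes PCT results from the primary endpoint. That requires completion to mean attendance at OP5, which the SAP does not say, and the denominators in bullets a, c and f point the other way. Only OP3A could be lost, since a woman who completed Cycle 4 stays in the population whatever happens in Cycle 5. One omitted failure would turn 25/26 (96.2%, exact 95% lower bound 80.4%) into 25/25 (lower bound 86.3%). But the failure would have to fall on the woman who leaves between OP3A and OP5A, and protocol Appendix 2 continues participants after a failed Ovaprene cycle. This supports defining the term, not a claim of bias in the primary result.

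**Conclusion.** The concern holds for the secondary summaries. SAP 3.4, SAP 3.6 and Tables 14.2.2.1 to 14.2.2.5 leave out safety-cycle FG and pH values, and residual FG from used devices, for women who stop before completing Cycle 4. That conflicts with protocol 14.2.3 and makes release results depend on later retention.

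The documents do not give attrition timing, so the size cannot be stated. Under the assumptions of 25 women in the PCT population and 5 to 10 further users, 17% to 29% of exposed women are missing. The figure could be nil if everyone who uses the device completes an Ovaprene PCT cycle.

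The analyses are descriptive and the raw values remain listed, so this is worth correcting but does not threaten the study's main conclusion. The undefined meaning of completion is a secondary matter of alignment within the SAP.

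**What to change.** 1. In SAP 4.2.1, set the population of Tables 14.2.2.1 to 14.2.2.5 to Treated with Ovaprene. Keep a PCT-based population for the four -5PMS tables (14.2.2.1-E, 14.2.2.1-NE, 14.2.2.2-E and 14.2.2.2-NE versions). Ten of the 14 tables change.
2. Amend the opening sentence of SAP 3.6 to match: the PCT population for the primary analyses and for FG associated with success, and Treated with Ovaprene for the other FG, pH and residual-FG analyses. SAP 3.1.3 already reports the number of non-missing values, so the wider label creates no difficulty at visits a woman did not reach.
3. In SAP 3.4, define the PCT population as enrolled women who used Ovaprene and have at least one evaluable sperm count at OP3A or OP3B, whether or not they attended OP5. This brings 3.4 into line with primary bullets a, c and f.
4. Label Graph 14.2.2 (vaginal pH at EVMS) in the same way. It now cites All Treated, which SAP 3.4 does not define.

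The cost is one population definition, one sentence, a set of labels and the matching program filters. No new data, visits or participants are needed.

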#### 14.2.3 Secondary Objective: Release of active component from device

The mean, median, SD, and IQR of ferrous gluconate values associated with fewer than 5 progressively motile sperm per HPF will be calculated across all women. The mean, median, SD, and IQR of ferrous gluconate values at each time point at which it is collected will also be calculated across all women. The mean, median, SD, and IQR of ferrous gluconate values in used devices will be calculated. The mean, median, SD, and IQR of cervical mucus and vaginal pH before and after sex in the absence of and the presence of the device will be calculated across all women.

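### The protocol plans ferrous gluconate and pH summaries over all women, but the SAP table list gives them only as separate EVMS and non-EVMS tables, so the all-women median and IQR are not produced

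*SAP*

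**What the plan says.** Protocol 14.2.3 plans mean, median, SD and IQR for three items over the whole study group: "ferrous gluconate values associated with fewer than 5 progressively motile sperm per HPF will be calculated across all women"; "ferrous gluconate values at each time point at which it is collected will also be calculated across all women"; and "cervical mucus and vaginal pH before and after sex in the absence of and the presence of the device will be calculated across all women". For a fourth item it says only that "ferrous gluconate values in used devices will be calculated", with no all-women wording.

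SAP 3.6, secondary items c to f, presents FG levels and pH by visit, or by visit and time point. It asks for no site split. For pH, EVMS is mentioned only because it has several time points within a visit. Items a and b, on the first hours after insertion, are expressly confined to one site.

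SAP 4.2.1 then lists FG in cervicovaginal fluid (CVF) as "Summary of the Levels of Ferrous Gluconate in CVF at Study Site EVMS" (14.2.2.1-E) and "Summary of the Levels of Ferrous Gluconate in CVF at Non-EVMS Sites" (14.2.2.1-NE), each with a -5PMS version for successful tests. Cervical FG follows the same pattern, for example "Summary of the Levels of Ferrous Gluconate in Cervix at Non-EVMS Sites", and so do cervical and vaginal pH, for example "Summary of Vaginal Lateral Wall pH Values at Non-EVMS Sites". No combined version of any of these is listed.

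**The concern.** The protocol's release objectives ask about the device: which pre-sex FG level goes with success (2a), how soon it is reached (2b), whether it persists late in wear (2c), what happens to it after sex (2d), and what the device does to pH (2e). If the table list is followed as written, the common-visit data for these questions are reported separately for two smaller groups, and the summary the protocol specified is not reported. The SAP gives no reason for the change.

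The protocol expects about 25 women to complete, so each part is small, and the -5PMS tables are restricted further to successful tests.

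**Working it through.** **1. Protocol against table list**

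| Protocol 14.2.3 item | SAP 3.6 text | SAP 4.2.1 tables |
|---|---|---|
| FG with <5 progressively motile sperm, all women | item c, by visit | 14.2.2.1-E-5PMS and -NE-5PMS (cervix: 14.2.2.2-E-5PMS and -NE-5PMS) |
| FG at each time point, all women | items d and e, by visit and time point | 14.2.2.1-E and -NE (cervix: 14.2.2.2-E and -NE) |
| Cervical and vaginal pH, all women | item f, by visit | 14.2.2.3-E and -NE; 14.2.2.4-E and -NE |
| FG left in used devices | item g | 14.2.2.5 and 14.2.2.5-Dur, not split by site |

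Count for 14.2.2.1 to 14.2.2.4: CVF 4 + cervix 4 + cervical pH 2 + vaginal pH 2 = 12 tables, of which 6 are EVMS, 6 are non-EVMS and 0 are pooled.

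**2. Where a split is unavoidable**

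Protocol 9.2 to 9.5 and Appendix 1 reserve the samples at 0.5, 1, 2, 4 and 6 hours for EVMS: pH at BP2, and vaginal FG and pH at OS1 and OP3. Those rows cannot be pooled. The following are sampled at every site:
- Vaginal FG and pH: OS1 before insertion, OS2 to OS5, OP1, OP2, OP3 at the PCT, OP4 and OP5.
- Vaginal pH also at BP1, BP2 at the PCT, and BP3.
- Cervical pH: BP1, BP2 at the PCT, BP3, OS1, OS3, OS5, OP1, OP2, OP3 and OP5.

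**3. What can be rebuilt from a pair of tables**

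With stratum sizes n1 and n2, means m1 and m2, and SDs s1 and s2:
- m = (n1·m1 + n2·m2)/(n1 + n2)
- s² = [(n1−1)s1² + (n2−1)s2² + n1(m1−m)² + n2(m2−m)²]/(n1 + n2 − 1)

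Both are exact. No such formula exists for the median or the quartiles. In an artificial skewed sample of 10 and 15 values (not trial data), the rebuilt mean and SD matched the pooled ones. The stratum medians were 9.82 and 8.76, and their size-weighted average was 9.18, but the median of all 25 values was 9.74.

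**4. Precision, for illustration**

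The plan states no precision figure, so there is nothing to reproduce. Inputs: N = 25 completers (Protocol 14.1); the EVMS share is assumed; equal SDs are assumed. The SE ratio is √(N/n), and the 95% half-width is t(0.975, n−1)·SD/√n. Pooled: SE 0.20 SD, half-width 0.41 SD.

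| EVMS/other | SE ratio to pooled | Half-width in SD |
|---|---|---|
| 5/20 | √(25/5) = 2.24; √(25/20) = 1.12 | 1.24; 0.47 |
| 10/15 | √(25/10) = 1.58; √(25/15) = 1.29 | 0.72; 0.55 |
| 12/13 | 1.44; 1.39 | 0.64; 0.60 |
| 18/7 | 1.18; 1.89 | 0.50; 0.92 |

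**5. How the SAP treats comparable outputs**

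The primary sperm proportion has an overall table (14.2.1.1) and a site split (14.2.1.1-E-NE). Visit attendance has an overall table (14.1.2) and an EVMS time-point table (14.1.2-E). Soluble markers and antibacterial activity have one table with no site split (14.3.5.9), although their sampling time does differ by site at BP2, OS1 and OP3.

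**The case against.** The strongest defence is that the sites differ by more than a few extra rows. Before the 24-hour visits (OS2, OP4, BP3), EVMS women have had up to five additional samplings, and their lavage falls at 6 hours rather than at the PCT or OS1. The protocol itself says lavage probably affects later samples. That warning, however, concerns later samples at the same visit, and in Appendix 1's recommended order FG and pH are taken before the lavage. The difference deserves a footnote at the 24-hour visits; it does not rule out pooling.

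The sperm reading behind the -5PMS tables is blinded only at EVMS (Protocol 10.4). That is a reason to show the split alongside, as the SAP does for the primary proportion, which uses the same reading and is also pooled.

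Several further points stand and set the limits of the concern:
- The mismatch lies in a list of titles. SAP 3.6 neither requires the split nor forbids pooling, by-subject listings are planned, and the table shells are a separate document not seen here.
- FG in cervical mucus is exploratory throughout (footnote to Protocol 9.4.1).
- These endpoints are descriptive. No test, planned interval or sample size depends on them.

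SAP 1.0 allows small departures from the SAP to be described in the study report. That does not cover this case, because here the SAP departs from the protocol.

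**Conclusion.** The gap is real and limited. Under the table list as written, the all-women median and IQR for FG and pH are not produced and cannot be rebuilt from the paired tables. The affected questions are the level associated with success (2a), its persistence late in wear (2c), the pH effect (2e), and the later time points of 2b and 2d.

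A reader might infer that every release objective is answered twice and that the trial yields no study-wide result. The documents do not support that. The early hours of 2b and 2d come from EVMS alone by design, residual FG in devices is not split, and the overall mean and SD can be recovered.

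Nor do the documents support a definite loss of precision. Its direction is certain. The range of 1.12 to 2.24 rests on assumed splits, equal SDs and 25 women, whereas these tables use women with at least one Ovaprene PCT cycle, whose number is not fixed.

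**What to change.** Add pooled versions of Tables 14.2.2.1, 14.2.2.1-5PMS, 14.2.2.3 and 14.2.2.4, restricted to the common time points in step 2 of the working, and name them as the protocol 14.2.3 analysis. Three details are needed:
- At BP2 and OP3 use the reading at the PCT, and at OS1 the reading before insertion. Do not use the average over time points that SAP 3.6 item f also calculates.
- Show quartiles for pH. The SAP's six-number summary defaults to minimum and maximum, while the protocol names the IQR.
- Footnote that EVMS women had extra sampling before OS2, OP4 and BP3.

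Keep the -E tables for the 0.5 to 6 hour series and the -NE tables as by-site support. Pooled cervical FG tables (14.2.2.2) may be added if labelled exploratory. The cost is a few extra table runs and no new data.
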